Appendix C. Perioperative Measures

Preoperative Measures

- Adjuvant behavioral or biofeedback in previous 30 days: type and # sessions

Operative Measures

For both procedures:

- Date of surgery
- Surgery performed (1. Burch, 2. sling)
- More than one surgery; specify (List: enterocele repair, colpopexy, cystocele and rectocele repair, vaginal or abdominal hysterectomy, hernia repair; paravaginal repair; other)
- Assistant: Resident, Fellow, non-study surgeon – level and specialty
- Operative time: enter OR, start incision, wound closed, leave OR
- Type of anesthesia (LIST: 1. General, 2. Spinal, 3. Epidural, 4. Sedation, 5. Local, 6. None)
- Estimated blood loss: ____ ml as recorded by anesthesiologist
- Blood transfusion: #units, autologous (Yes, No)
- Suture material and gauge
- Intraoperative complications (e.g., urethral or bowel injury) [see Appendix B]
- Urine drainage: SP tube, urethral catheter, no catheter
- Cystoscopy: abnormal findings; describe intraoperative and corrected complications
- Was randomization violated, i.e., any deviation from randomized procedure

For Burch procedures

- Suture material and gauge
- Number sutures on each side
- Length of abdominal incision
- Orientation of incision: vertical, horizontal, other
- One vs. two passes through Cooper's ligament

For sling procedures

- Sling material: autologous fascia (rectus; if fascia lata, specify reason)
- Size of sling material: ____ cm long x ____ cm wide
- Suture of sling material: simple one stitch, two stitches, helical x3, other
- Abdominal incision
 - Length of incision
 - Orientation of incision: vertical, horizontal, other
- Device to pass suture/sling from vagina to site of anchoring: specify device [LIST: Stamey needle, commercial device. If commercial device, specify name of device and brand.
- Folding of sling ends: Yes/No
- Tied suture over/to rectus fascia

Post-Operative Measures

- Complication(s): specify (see Appendix B)
 - In recovery room
 - First 24-hours after leaving recovery room
- Fever > 101°F, 38.3°C during hospitalization: specify
- Blood transfusion during hospitalization: # units, autologous (Yes, No)
- Length of hospitalization
- Audit of discharge medications
- Voiding at discharge
- Estimated residual urine volume
- Discharge with catheter: SP tube, urethral, clean self cath, none
- Pain

Perioperative Measures through 3 months

- Physician visits: number, reason
- Complications: specify
- Readmissions: date, reason, LOS for each
- Emergency room admissions: date, reason for each
- Additional abdominal or pelvic surgery: date, procedure, reason
- Medication Audit
 - Antibiotics: type, # days
 - Pain med: type, # days, # pills
- Resumption of spontaneous voiding
 - If catheter at discharge: date removed, residual urine volume at removal
 - If intermittent catheterization, when stopped
- Urine incontinence: frequency, type
- UTI: dates and treatment
- Persistent pain at site of surgery: duration, description
- Number of lost work days
- Resumption of normal activities

Measures for all Follow-up Points

- Persistent pain at site of surgery (i.e. >6months = “complication”)
- Develop hernia: describe
- Develop vaginal prolapse: describe – POP-Q and self-report
- Develop new UI: describe
- Change in bowel movements: describe
- Develop new fecal incontinence: describe
- Develop new sexual dysfunction: describe

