An independent group of experts in urology, urogynecology, biostatistics, clinical trials, behavioral medicine, nursing, and ethics who are not otherwise involved in the study has been appointed by the NIDDK to review periodically the progress of the study. Such monitoring will include at least the following: review of study protocols prior to implementation; monitoring of patient accrual; review of reported adverse events; monitoring of protocol compliance; review of data analysis plans; monitoring data quality, and interim monitoring of study endpoints.

PROTOCOL

A. STUDY AIMS

The primary aim of this randomized clinical trial is to compare the Burch modified Tanagho and autologous fascia sling procedures for overall treatment success and stress-related symptoms at a minimum of 24-months post-surgery in women with predominant stress incontinence.

The secondary aims of the trial are:

- to compare complications including voiding dysfunction, quality of life, sexual function, satisfaction with treatment outcome, and need for additional surgery or other postoperative treatment for the two surgical procedures;
- to determine the prognostic value of urodynamic studies and to identify urodynamic parameters that predict treatment success in each surgical procedure.

B. BACKGROUND AND SIGNIFICANCE

B.1 Urinary Incontinence: Prevalence and Impact

Of the estimated 16 million Americans who suffer from urinary incontinence (Fantl, Newman, Colling, & al, 1996), two-thirds are women. Individuals with incontinence suffer social isolation, sexual and relationship dysfunction, and depression (Hunskar & Vinsnes, 1991). The monetary cost to society is over \$26 billion annually; most of this money is spent on the consequences of incontinence, not on its treatment (Wagner & Hu, 1998). Urinary incontinence remains an under-reported and under-treated condition. Patients suffer in silence because they think incontinence is a normal part of aging, or they feel embarrassed to discuss the problem with their physician (Norton, MacDonald, Stanton, & Sedgwick, 1988). In spite of these staggering statistics, there have been surprisingly few rigorously conducted scientific studies on the epidemiology, etiology or treatment of incontinence. The field suffers from a general lack of uniformity and standardization in the incontinence literature.

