This randomized clinical trial of the Burch modified Tanagho vs. the autologous fascia sling procedures compares outcomes beyond cure, such as post-operative voiding dysfunction, *de novo* detrusor instability, hospitalization time, recovery time, and quality of life. The prognostic value of pre-operative urodynamic testing (which has never been demonstrated prospectively) and identification of urodynamic parameters which predict surgical success will also be investigated. The importance of these secondary outcomes is illustrated by a recent decision analysis by Weber and Walters (2000). They compared the effectiveness and cost of Burch colposuspension and sling procedures for primary surgical treatment of genuine SUI in women. Exploring the clinical belief that the increased success rates for slings are associated with higher complication rates, these Investigators decided that the two procedures were equivalent in overall effectiveness, but that complications of retention and *de novo* detrusor instability did influence the decision analysis. Using estimates of outcomes and complications from mostly clinical series and some estimates from expert opinion, they concluded that the Burch colposuspension was the superior procedure when the risk of retention after sling was higher than 9.0%, or when the risk of *de novo* detrusor instability after sling was higher than 10.3%. The pubovaginal sling was superior when the risk of *de novo* detrusor instability after Burch was higher than 6.8%. The authors recommended that until a randomized clinical trial can be accomplished, individual surgeons should consider their complication rates when deciding on which procedure to use.

Tension-free vaginal tape (TVT) is a newer procedure that has experienced recent commercial success in Europe and the United States. A review of this procedure was presented by the manufacturer at the July 2001 International Consultation on Incontinence, and fewer than 200 cases were presented for long-term (i.e. five year) follow-up. Thus, the data are considered

too preliminary and the experience too recent to include TVT in a randomized trial at the present time.

[figure not shown]
B.4 Advantages of a Randomized Clinical Trial

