Intervening variables that might affect the outcomes of interest consist of the following four categories:

- *Pelvic comorbidity*: pelvic organ prolapse (POP-Q quantification)
- *Intraoperative considerations*: surgical and medical complications (see Appendix B); length of procedure; estimated blood loss (see Appendix C)
- *Postoperative considerations*: length of hospital stay; post-operative pain; medical complications (e.g., pulmonary, febrile morbidity, cardiovascular, neurologic, urinary tract; see Appendix B); de novo or recurrent urinary urgency or urge incontinence; other non-surgical treatments
- *Patient expectations of surgery*

H.5 Schedule of Measurements

The schedule of measurements is included in Appendix A. Data will be collected during clinic visits at baseline, 6-weeks, 6-months, 12-months, and 24-months, and by mail or telephone at 3-months and 18-months.

For those patients determined to be a treatment failure because of surgical retreatment for SUI, the 24-month assessment battery will be completed at the time that this surgical retreatment is determined necessary (i.e. before the surgical retreatment). Follow-up visits will continue as scheduled with one exception to the assessment battery at 24 months, i.e. UDS will not be required at 24-months as testing was conducted prior to surgical retreatment. For those patients determined to be a treatment failure for all other reasons, the 24-month assessment battery will be completed at the time that this treatment is determined necessary, but further follow-up assessments will continue as scheduled. If the

out-of-sequence 24-month assessment is performed within the specified window for the next assessment, then that next assessment can be omitted.

If more than 6 months transpires between determination of eligibility and surgery, the following measures must be repeated to ensure current eligibility for the trial as well as to obtain current baseline values for critical measures that would be subject to change over a 6-month period.

- 1) The MESA assessment (Data Form 01, Sections C and D),
- 2) Recent pelvic surgery (Data Form 02, Section C),
- 3) Medication Audit (Data Form 03),
- 4) POP-Q examination (Data Form 04, Section E),
- 5) The Pad Test (Data Form 06, Section B),
- 6) The Voiding Diary (Data Form 06, Section C),
- 7) Expectations of Surgery (Data Form 07, Section B),
- 8) Quality of Life (Data Form 07, Section C),
- 9) Normal Activities (Data Form 07, Section D),

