Fisher's exact test will be used for unadjusted analysis of the primary endpoints and other dichotomous outcomes (e.g. complication rates). Time-to-failure analyses (Kaplan-Meier plots and logrank tests) will also be used in secondary analyses of the primary outcome as described above under "Interim Monitoring." Treatment comparisons will be adjusted for covariates with the logistic model for dichotomous endpoints and proportional hazards models for time-to-failure analyses. Analysis of continuous outcomes such as the quality of life subscales will be based on change from baseline. Prognostic models will be developed using baseline urodynamic testing results and other baseline covariates to explore the extent to which baseline measures can be used to predict surgical success. Time-to-event methods will be utilized to characterize time to normal voiding. In addition to comparing treatment groups with respect to satisfaction with surgery, the analysis of this outcome will include an evaluation of expectations of surgery as a predictor of satisfaction.

L. RECRUITMENT

To assess ability of the nine clinical centers to enroll the required number of patients (73 patients per center) into the trial over a two-year period, each center provided data in July 2001 regarding the number of Burch and sling procedures performed over the prior 12-months. These data are displayed in Table 2. Based on these data and the estimated enrollment rate of 20% of eligible patients, there appear to be a sufficient pool of patients from which to recruit. In the event that the enrollment rate has been overestimated (i.e. fewer patients agree to participate in the trial), several additional sources of potential patients have been identified:

- Investigator's office (might include patients of a non-study surgeon in a group practice);
- Referrals from colleagues;
- Post-card announcements in clinical areas/offices;
- Advertising: newspapers; newsletters; cable TV or public service announcements; websites of professional organizations, advocacy groups, or NIH; health fairs, health clubs, billboards;
- Mailings to enriched lists, e.g., former patients.

Table 2. Number of Procedures by Site: Approximate 12 Months prior to July 2001

Site	Burch	Sling
University of Alabama - Birmingham	68	162
University of California - San Diego	123	152
University of Maryland	46	155
University of Pittsburgh	33	297
University of Texas - Dallas	141	102

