Appendix D. Guidelines for Post-Operative Instructions

ACTIVITY:

Rest as much as needed during the first two weeks after your procedure.
Avoid heavy lifting, pushing or pulling.
Lifting: Limit your lifting to about 10 lbs for the first 4-6 weeks post-op (About a gallon of milk).
Discuss heavier lifting with your doctor at your post-op visit.
Avoid standing for prolonged periods of time.
Climbing stairs is allowed.
Talk to your doctor about when you may resume usual physical activity.

NUTRITION:

Resume your normal diet.
Drink 6-8 glasses of non-caffeinated beverages daily.
Eat a well-balanced diet.

ELIMINATION:

It is important not to strain during bowel movements.
Narcotics tend to make you constipated.
Preventing constipation is easier than treating it!
Eat a high fiber diet (fruits, vegetables, and bran).
Take a stool softener once or twice daily.

If constipation should occur:

You may take a mild laxative (Milk of Magnesia).
Add fruit and bran to your diet.
Drink more liquids.

Call your doctor or nurse if you experience burning on urination or urgency frequency or you feel that you are unable to completely empty your bladder.

VOIDING:

Avoid bladder distension.
Void every 2-3 hours, whether you feel like you have to or not.
Your sensation of fullness may be altered by anesthetics, swelling or repositioning of a previously prolapsed bladder.
If additional bladder care is required, you will receive instructions from your doctor or nurse.

HYGIENE:

You may shower and wash your hair. If your incisions are closed, you may bathe unless your doctor tells you otherwise. Do not douche or use tampons until after your follow-up appointment.

FEVER:

If you feel feverish or have shaking chills, take your temperature. If your temperature is 100.4°F (38°C) or above, call your doctor. The fever may mean there is an infection.

ABDOMINAL INCISION CARE:

Clean the incision with water. Do not use a dressing unless the incision is draining or irritated. If you have small adhesive strips in place, and they do not fall off within 10 days, carefully peel off. Check your incision daily for redness, draining, swelling or separation of the skin. Call your doctor if you notice any of these.

VAGINAL DISCHARGE:

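### Minor: the only fever item stops at discharge, so if length of stay differs by procedure, a crude comparison of in-hospital fever compares unequal observation windows

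*Protocol*

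**What the plan says.** Section A makes complications a secondary comparison: "to compare complications including voiding dysfunction, quality of life, sexual function, satisfaction with treatment outcome". Section K.3 sets the test: "Fisher's exact test will be used for unadjusted analysis of the primary endpoints and other dichotomous outcomes (e.g. complication rates").

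Section H.4 lists, under post-operative considerations and alongside length of hospital stay, "medical complications (e.g., pulmonary, febrile morbidity, cardiovascular, neurologic, urinary tract; see Appendix B"). Appendix B lists infections such as pneumonia, cystitis and pyelonephritis, but not fever.

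The one place where fever is a data item is the post-operative list in Appendix C: "Fever > 101°F, 38.3°C during hospitalization: specify". The same list records "Length of hospitalization". Section B.3 names, among the outcomes beyond cure that the trial compares, "hospitalization time, recovery time, and quality of life". No section fixes a day of discharge.

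After discharge, Appendix C collects through 3 months physician visits with reason, complications, readmissions, emergency visits, antibiotics and urinary tract infections. Appendix A schedules complications at 6 weeks and at every later contact. None of these is a fever field.

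**The concern.** The time during which a fever can be recorded equals the length of stay, and that may differ by procedure. A woman who goes home on day 2 and has a fever on day 3 without seeking care leaves no fever record. A woman with the same fever who is still in hospital does leave one. A comparison of crude proportions then mixes the frequency of fever with the time under observation, and the procedure with the longer stay can look worse on this complication.

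The reference from H.4 to Appendix B does not help, because the complications list that staff work from does not mention fever. Later analysis cannot recover a post-discharge fever that no form asks about. At stake is one safety comparison under the secondary aim.

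**Working it through.** The protocol states no figure on this point, so there is nothing to reproduce. What follows is an illustration of size.

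**Input from the protocol:** 325 women per group (K.1).

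**Assumptions, none of them in the protocol:**
- The true 14-day fever risk is R = 10% in both arms.
- The stay is a fixed 2 days in one arm and 3 (or 4) in the other, and does not depend on fever.
- Fever onset either declines exponentially after surgery, with scale m = 1, 2 or 5 days and cut off at 14 days, or is spread evenly over 14 days.

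**Formulas.** The share of fevers that have started by day t is F(t) = (1 − e^(−t/m)) / (1 − e^(−14/m)), or t/14 if onset is even. The recorded rate is R × F(stay), so the rate ratio is F(longer stay) / F(shorter stay).

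**Worked line, m = 2:** F(2) = 0.6321/0.9991 = 0.633 and F(3) = 0.7769/0.9991 = 0.778. Recorded rates are 6.33% and 7.78%, a ratio of 1.23 and a difference of 1.4 points.

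The last two columns give the chance that the two-sided Fisher test at 5% is significant. It is obtained by summing binomial probabilities over all tables with p ≤ 0.05 at 325 per arm.

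| Onset | F(2) | F(3) | Recorded, 2 vs 3 days | Ratio | Difference (points) | Significant, 2 vs 2 days | Significant, 2 vs 3 days |
|---|---|---|---|---|---|---|---|
| m = 1 day | 0.865 | 0.950 | 8.65% vs 9.50% | 1.10 | 0.9 | 4% | 5% |
| m = 2 days | 0.633 | 0.778 | 6.33% vs 7.78% | 1.23 | 1.4 | 3% | 8% |
| m = 5 days | 0.351 | 0.480 | 3.51% vs 4.80% | 1.37 | 1.3 | 3% | 9% |
| even over 14 days | 0.143 | 0.214 | 1.43% vs 2.14% | 1.50 | 0.7 | 2% | 6% |

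For stays of 2 versus 4 days, the ratio runs from 1.14 (m = 1) to 2.00 (even onset). With equal stays it is 1.00 in every row. A fixed window in which fever is equally well detected in both arms also gives 1.00, whatever the stays.

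**The case against.** The strongest reply is that this item matters little and that other items cover part of the gap. Febrile morbidity is an example under intervening variables, not a named outcome, and K.3 names no test for fever in particular. Fever that leads to a visit, a readmission, antibiotics or a listed infection can be recorded through 3 months. The protocol does not predict that either procedure has the longer stay, and if nearly all fevers start before the earlier discharge, little is lost. All of this stands, and it is why the point is minor. It does not close the gap: those items record care and diagnoses, not temperature, and H.4 itself calls febrile morbidity a medical complication, which Section A compares. Length of stay is recorded, but adjusting for it is not a clean repair, because a fever can itself prolong the stay.

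Some stronger readings are tempting, but the documents do not support them:

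- **That the longer-stay arm must show more fever, or that false positives would be frequent.** A constant daily chance of 2% to 6%, with stays from 1.5 vs 2.0 up to 2.0 vs 3.5 days, gives rejection rates of 7% to 76%. Such a chance never declines after surgery. Continued for 14 days, 1 − (1 − h)^14 is 25% at h = 0.02 and 58% at h = 0.06. No figure in the protocol supports this.
- **That transfusion has the same flaw.** Appendix C has an in-hospital transfusion item, but Appendix B also lists need for transfusion with no in-hospital limit.
- **That the two temperatures conflict.** Appendix D tells the patient: "If your temperature is 100.4°F (38°C) or above, call your doctor". That is an instruction in an optional guideline. The Appendix C figure defines a data item. The two serve different purposes.

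**Conclusion.** The point holds in a conditional form and is minor. The fever item has no fixed window and no post-discharge counterpart, and the reference from H.4 to Appendix B leads to no fever entry. A crude between-arm comparison of in-hospital fever is biased against the longer-stay arm if two things are true: stays differ by procedure, and some fevers start after the earlier discharge. The protocol establishes neither.

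Under the assumed 10% risk and stays of 2 versus 3 days, the recorded ratio is about 1.1 to 1.5, and the chance of a significant Fisher result is about 5% to 9%, against 2% to 4% with equal stays. These figures depend on assumed risk, onset and stay, and show scale only. The effect is confined to one safety descriptor; the primary endpoints, sample size and type I error of the main comparison are unaffected.

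**What to change.** 1. In Appendix C, record the date of each fever.
2. Compare the arms over a fixed post-operative window that is the same for all women, stated in days from surgery and not in terms of discharge.
3. Add a fever item, with the data definition already used in Appendix C, to the complications asked at the 6-week visit.
4. List fever in Appendix B, so that the reference in H.4 has a target.
5. Report in-hospital fever as description only, next to length of stay.

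The cost is one date field, one item at a visit that already takes place, and one line in Appendix B. Section J says the DSMB approved the list of reportable events, so the added line should go to the DSMB. Appendix D need not change.

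The limit should be stated with the result. Fever at home is self-measured and less completely detected than fever in hospital, so detection still depends partly on stay. The 6-week comparison therefore reduces the bias but does not fully remove it.

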Appendix D. Guidelines for Post-Operative Instructions

ACTIVITY:

Rest as much as needed during the first two weeks after your procedure.
Avoid heavy lifting, pushing or pulling.
Lifting: Limit your lifting to about 10 lbs for the first 4-6 weeks post-op (About a gallon of milk).
Discuss heavier lifting with your doctor at your post-op visit.
Avoid standing for prolonged periods of time.
Climbing stairs is allowed.
Talk to your doctor about when you may resume usual physical activity.

NUTRITION:

Resume your normal diet.
Drink 6-8 glasses of non-caffeinated beverages daily.
Eat a well-balanced diet.

ELIMINATION:

It is important not to strain during bowel movements.
Narcotics tend to make you constipated.
Preventing constipation is easier than treating it!
Eat a high fiber diet (fruits, vegetables, and bran).
Take a stool softener once or twice daily.

If constipation should occur:

You may take a mild laxative (Milk of Magnesia).
Add fruit and bran to your diet.
Drink more liquids.

Call your doctor or nurse if you experience burning on urination or urgency frequency or you feel that you are unable to completely empty your bladder.

VOIDING:

Avoid bladder distension.
Void every 2-3 hours, whether you feel like you have to or not.
Your sensation of fullness may be altered by anesthetics, swelling or repositioning of a previously prolapsed bladder.
If additional bladder care is required, you will receive instructions from your doctor or nurse.

HYGIENE:

You may shower and wash your hair. If your incisions are closed, you may bathe unless your doctor tells you otherwise. Do not douche or use tampons until after your follow-up appointment.

FEVER:

If you feel feverish or have shaking chills, take your temperature. If your temperature is 100.4°F (38°C) or above, call your doctor. The fever may mean there is an infection.

ABDOMINAL INCISION CARE:

Clean the incision with water. Do not use a dressing unless the incision is draining or irritated. If you have small adhesive strips in place, and they do not fall off within 10 days, carefully peel off. Check your incision daily for redness, draining, swelling or separation of the skin. Call your doctor if you notice any of these.

VAGINAL DISCHARGE:

If you have vaginal incisions, you may have bleeding and vaginal discharge for several weeks. If it is heavier than a normal period, call your doctor. Keep track of when the bleeding began and how many pads you have used that day. If you are still bleeding, try to remember when your last period began. This new bleeding may be your period.

PERI-CARE:

Keep your perineal area (the area between the vagina and the rectum) clean and dry. Perform peri-care after every bowel movement and each time you urinate. You may take a sitz bath or sit in a tub of clean warm water when necessary, unless your doctor tells you otherwise.

SEXUAL INTERCOURSE:

If you have an incision in your vagina you should not have sexual intercourse until your doctor tells you otherwise at your post-op visit.

PAIN CONTROL:

Most surgical procedures are associated with some degree of pain.

Follow your doctor's instructions regarding pain medications.

Poorly controlled pain in the perineal or vaginal area may contribute to your inability to urinate or have a bowel movement because of muscle spasms.

You may also take acetaminophen (Tylenol) or ibuprofen (Advil or Motrin).

Avoid aspirin.

Your need for pain medication will decrease over time.

If pain is not relieved by the medication, or the pain gets worse, call your doctor, as this may be a sign of infection.
